6.6.2 Dose Reduction

Dose reduction is defined as 1) decreased in the total daily dose level or, 2) a decrease in the frequency of dosage (BID to QD for example)

6.6.3 Dose Increase

A dose increase is defined as 1) increase in the total daily dose or, 2) an increase in the frequency of dosage (QC to BID for example). A dose increase may be allowed at the discretion of the Investigator with Sponsor approval. A Participant may be eligible for a dose increase if:

- Completed at least 1 cycle of treatment
- Did not experience any Grade >2 or any significant, unacceptable, or irreversible toxicities considered related to the trial interventions.
- Have not required any prior dose reductions.

All available safety [REDACTED] data will be used to determine intraparticipant dose escalations. Dose may only be escalated to a level that has been declared safe and tolerable by the SRC. Participants will be annotated with “Intraparticipant dose escalation” and will not be considered part of the DLT-Evaluable population at the dose the participant was escalated to.

[REDACTED] safety data may be evaluated to increase the frequency of the dose, only after agreement with the SRC.

6.6.4 Actual Cumulative Dose

The actual cumulative dose of RP-3467 or olaparib is defined as the sum of all actual doses administered taking into consideration of any dose change during the study treatment exposure. Information on dose modifications, including dose increases, reductions, and interruptions will be recorded in the CRF. Modifications will be recorded with their start and end dates, as well as the reason for dose change, this information will be used to determine the total cumulative dose over the course of treatment exposure.

6.6.5 Actual Dose Intensity

[figure not shown]
The actual dose intensity (ADI) is defined as the actual cumulative dose during a cycle, calculated only for those patients who started cycle 1 treatment as :

[figure not shown]
$$\text{RP-3467 or olaparib ADI (mg/cycle)} = \frac{\text{Actual Cumulative Dose (mg)}}{\frac{\text{Duration of exposure (days)}}{\text{planned cycle length } \left(\frac{\text{days}}{\text{cycle}}\right)}}$$

[figure not shown]
6.6.6 Relative Dose Intensity

[figure not shown]
The Relative Dose Intensity (RDI) is defined as the ADI divided by Planned Dose Intensity (PDI) and reported as Percentage. The PDI is defined as the initial dose of the study drug multiplied by planned number of dosing days per cycle according to the protocol. The planned cycle length (days) is 21 days. Initial dose is the dose per day which was intended to be administered at the start of the planned dose regimen. For RDI will be summarized for Cycle 1, as well as across the entire treatment period. Subjects that crossed over from monotherapy to combination therapy, RDI is only calculated up to the start of the rescue treatment period.

[figure not shown]
Details of study treatment exposure will be listed for Safety Population and swimmer plot for duration of treatment for individual participants by arm, dose level, and dose schedule will be presented.

10.SAFETY ANALYSIS

10.1 Dose Limiting Toxicities (DLT)

The number of DLTs will be summarized by treatment arms for the DLT Evaluable Population. A toxicity will be considered a DLT if it occurs from the first dose to the end of Cycle 1 [REDACTED]
[REDACTED], meets the pre-defined criteria for DLTs, is deemed at least possibly related to trial treatment, and is not clearly and incontrovertibly due to disease progression or extraneous cause. Toxicity will be assessed using CTCAE v5.0, unless other specified. Details of DLTs will be listed.

DLTs will be defined as any of the following:

- Any death not clearly due to the underlying disease or extraneous causes

Hematologic TEAEs:

- Grade 4 neutropenia
- Febrile neutropenia (defined as absolute neutrophil count (ANC) <1000 cells/ μ L with a single temperature of 38.3°C [100.4°F] for > 1 hour).
- Grade 4 thrombocytopenia or Grade 3 thrombocytopenia associated with Grade \geq 2 bleeding.
- Grade 4 anemia or Grade 3 anemia requiring red blood cell (RBC) transfusion given to participants with documented anemia-related symptoms.

Non-Hematologic TEAEs:

- Any Grade \geq 3 TEAE except the below
 1. Grade \geq 3 non-hematologic laboratory abnormalities that are asymptomatic and respond to medical intervention or resolve to grade 1 in \leq 72 hours.
 2. Grade 3 fatigue with duration < 7 days
 3. Grade \geq 3 nausea/vomiting/diarrhea that lasts \leq 72 hours and resolves with or without optimal supportive care.
 4. Grade \geq 3 amylase or lipase elevation not associated with symptoms or clinical manifestations of pancreatitis.
 5. The use of red blood cell transfusion for anemia Grade <3 or the use of G-CSF for Grade <4 neutropenia
- Symptomatic Grade \geq 3 QTc prolongation (QTcF \geq 501 msec on at least two separate ECGs), or asymptomatic Grade \geq 3 QTc prolongation that has been confirmed by repeat testing and reevaluation by a qualified person and persists after correction of reversible causes such as electrolyte abnormalities or hypoxia.
- Drug-induced liver injury meeting Hy's Law criteria defined as:
 1. ALT or AST \geq 3-fold above the Upper Limit of Normal (ULN) or \geq 5.0 x ULN in the case of liver metastases at baseline and
 2. Serum total bilirubin \geq 2-fold above ULN (without findings of cholestasis) and

3. Alkaline phosphatase < 2 x ULN and
4. No other overt reason for liver injury

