The BOIN design will guide dose level escalations/de-escalations using the following rules for both Arm 1 (RP-3467 monotherapy) and Arm 2 (RP-3467 with olaparib), targeting a 25% DLT rate:

- If the observed DLT rate at the current dose is ≤ 0.197 , escalate the dose to the next higher dose level;
- If it is > 0.298 , de-escalate the dose to the next lower dose level;
- Otherwise, stay at the current dose.

A 3+3 decision criteria will be applied if the number of participants treated at the current dose is 3. Meaning, if 0/3 participants experience a DLT at the current dose, then the dose will be escalated. If 1/3 participants experience a DLT, then the dose will stay at the current level, and the dose will de-escalate if $\geq 2/3$ participants experience a DLT. The rules for dose escalation/de-escalation can be summarized in the following table.

Table 2: Dose Escalation/De-Escalation Rules for the BOIN Design

Action	Number of DLT Evaluable Participants at Current Dose Level								
	1	2	3	4	5	6	7	8	9
\uparrow if number of DLT \leq	0	0	0	0	0	1	1	1	1
\downarrow if number of DLT \geq	1	1	2*	2	2	2	3	3	3
Elim if number of DLT \geq	NA	NA	3	3	3	4	4	4	5

BOIN = Bayesian optimal interval; \uparrow = increase, \downarrow = decrease, DLT = dose-limiting toxicity, Elim=eliminate, NA = not applicable, dose cannot be eliminated until at least 3 participants have been treated and are DLT evaluable
Note: # of DLT is the number of participants with at least 1 DLT. When none of the actions (i.e., escalate, de-escalate or eliminate) is triggered, stay at the current dose for treating the next cohort of participants.

* Based on the 3+3 design run-in.

If a determination is made to eliminate based on the criteria in Table 2, then the current dose and all higher concentrations are eliminated, and the dose is automatically de-escalated one level. If none of the actions (escalation, de-escalation, elimination) are triggered, participants will continue to be enrolled at the current dose. Dose escalation/de-escalation will continue until the maximum total sample size is reached (n~36), 9 participants are enrolled at the current dosing level and the decision is made to maintain the current dose according to the rules outlined in Table 2, or the SRC decides to stop.

Monotherapy dose escalation may be stopped before establishment of an MTD if

- MTD is exceeded in the combination dose-escalation arm

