2.3 Sample Size

The approximate total number of participants for this trial is 52 evaluable patients. This will include approximately 36 participants in dose escalation (both monotherapy and combination therapy) and 16 participants in backfill cohorts. Additional participants may be added to account for non-DLT evaluable participants in the dose escalation cohorts and participants in backfill cohorts with less than 1 full cycle of treatment.

[figure not shown]
The sample size for dose escalation is not driven by statistics but determined based on number of dose escalations that will potentially be assessed. It is estimated that approximately 12 participants (up to 4 dose levels) are needed for the monotherapy dose escalation (Arm 1) due to the minimum toxicity expected, and approximately 24 participants for the combination escalation phase (Arm 2) with estimated up to 5 potential dose levels for the combination.

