3.2 Endpoints

3.2.1 Primary Endpoints

- DLTs, incidence and severity of TEAEs

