4.1 DLT Evaluable Population

The DLT Evaluable Population will consist of participants who have met the minimum safety evaluation requirements of the trial and /or who experience a DLT at any time during the DLT evaluation period (from the start of treatment through the end of Cycle 1). Minimum safety requirements will be met if, during Cycle 1 of treatment, the participant receives at least 75% of their planned total dose of RP-3467 and olaparib (if applicable), completes required safety evaluations and is observed through the end of Cycle 1 since the first dose of trial intervention. Administration of growth factors or transfusions during the DLT evaluation period for hematologic events not meeting DLT criteria will render a participant not DLT evaluable. DLT evaluability will be recorded in the appropriate CRF and used to determine the DLT evaluable population. The DLT evaluable population will be used to determine DLT rate of the dose levels.

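### The febrile-neutropenia DLT in SAP 10.1 gives one fever threshold as two temperatures that differ by 0.3°C, and does not say how the one-hour condition applies

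*SAP*

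**What the plan says.** SAP 10.1 lists the haematologic events that count as DLTs. One entry begins "Febrile neutropenia (defined as absolute neutrophil count (ANC) <1000 cells" per µL and adds the fever condition "with a single temperature of 38.3°C [100.4°F] for > 1 hour". No comparator is printed before the temperature. SAP 10.1 adopts CTCAE v5.0 for toxicity except where specified otherwise, and for this item it prints its own definition. No other part of the supplied protocol or SAP gives a fever threshold.

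The definition is used in three places:

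- SAP 3.2.1 names the primary endpoints as "DLTs, incidence and severity of TEAEs".
- SAP 2.1 applies the count of participants with a DLT to Table 2. For a cohort of three, for example, "if 0/3 participants experience a DLT at the current dose, then the dose will be escalated".
- SAP 4.1 uses the DLT evaluable population to obtain the DLT rate at each dose level. It also says that giving growth factors or transfusions "for hematologic events not meeting DLT criteria will render a participant not DLT evaluable".

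**The concern.** A threshold given in two units has to be one temperature. Here a reader using Celsius and a reader using Fahrenheit apply different cut-offs to the same participant. The protocol synopsis describes a multi-site, multi-regional trial, and the supplied text does not fix the unit in which temperatures are recorded.

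The duration wording adds a smaller ambiguity. A single temperature is one reading, whereas a condition lasting more than an hour needs either repeated readings or a rule for inferring persistence. The text does not say which is meant.

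At stake is the DLT count. It is a primary endpoint, it decides escalation in cohorts as small as three, and under SAP 2.1 it can feed the isotonic estimate used to determine the MTD. The classification can also change the denominator. If growth factors are given and the event is judged not to be a DLT, SAP 4.1 removes the participant from the evaluable set.

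**Working it through.** **Inputs.** The 38.3°C and 100.4°F figures are from SAP 10.1. The escalate, de-escalate and eliminate boundaries are from SAP Table 2.

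**1. Conversion.**

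- °F = °C × 9/5 + 32: 38.3 × 9/5 + 32 = 100.94°F, not 100.4°F.
- °C = (°F − 32) × 5/9: (100.4 − 32) × 5/9 = 38.0°C, not 38.3°C.
- Gap: 38.3 − 38.0 = 0.3°C; 100.94 − 100.4 = 0.54°F.

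**2. Could rounding explain it?**

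- 38.3°C to one decimal covers 38.25 to 38.35°C, which is 100.85 to 101.03°F.
- 100.4°F to one decimal covers 100.35 to 100.45°F, which is 37.97 to 38.03°C.
- The ranges do not overlap, so rounding is excluded.

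**3. Who is affected.** Reading each figure as *at or above*, this is a participant who in Cycle 1 has an event at least possibly related to treatment, a neutrophil count below 1000 cells/µL, a fever from 38.0°C to just under 38.3°C, and no Grade 4 neutropenia (a DLT in itself) or other DLT.

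**4. Effect of one reclassified participant on Table 2.** The table compares k DLTs with k + 1 at the same n.

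| n | 0 vs 1 | 1 vs 2 | 2 vs 3 |
|---|---|---|---|
| 3, 4, 5 | escalate / stay | stay / de-escalate | de-escalate / eliminate |
| 6 | escalate / escalate | escalate / de-escalate | de-escalate / de-escalate |
| 7, 8, 9 | escalate / escalate | escalate / stay | stay / de-escalate |

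- The action changes in 3 + 7 + 6 = 16 of 21 cells.
- The next dose changes in 3 + 7 + 3 = 13 of 21. In the other three (2 vs 3 at n = 3, 4, 5) the next dose is the same, because on elimination "the current dose and all higher concentrations are eliminated, and the dose is automatically de-escalated one level". Elimination does also close the current and higher doses.
- Over every count from 0 to n − 1 (3 + 4 + … + 9 = 42 cells), the action changes in 20 and the next dose in 13.

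These are counts of table cells, not probabilities. They would be the same for any single misclassified DLT.

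**5. Effect if the participant is removed instead.** SAP 2.3 allows replacement: "Additional participants may be added to account for non-DLT evaluable participants in the dose escalation cohorts". The result therefore depends on what follows.

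| Counted as DLT | Removed, not replaced | Replaced, no DLT | Replaced, DLT |
|---|---|---|---|
| 1/3 stay | 0/2 escalate | 0/3 escalate | 1/3 stay |
| 2/3 de-escalate | 1/2 de-escalate | 1/3 stay | 2/3 de-escalate |
| 1/6 escalate | 0/5 escalate | 0/6 escalate | 1/6 escalate |
| 2/6 de-escalate | 1/5 stay | 1/6 escalate | 2/6 de-escalate |

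**The case against.** The strongest case on the other side concerns cause and consequence, not the arithmetic.

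- **Extraction.** The supplied text was read from PDF and has misread characters elsewhere, for example in the name of the BOIN design in the protocol synopsis. 38.3°C is 100.9°F to one decimal, one digit away from the printed figure. Alternatively, words may be missing between two separate criteria, which would also explain the awkward duration phrase. Neither can be shown or excluded, so the source PDF must be checked first.
- **The protocol's DLT section is not supplied.** SAP 10.1 governs how DLTs are summarised and listed. If the protocol's definition is clean and adjudication uses it, the effect stops at the SAP's DLT summary and listing. This limit stands.
- **Rarity and oversight.** Several conditions must coincide within a 0.3°C band. BOIN guides decisions that the Safety Review Committee also reviews, and the dose level N triggers include haematological toxicity of Grade 3 or above and any event the committee judges to limit tolerability. A case missed as a DLT need not go unnoticed. This makes a silent wrong escalation less likely, but it does not correct the DLT count.
- **Weight of the cell counts.** 16 of 21 can read as high impact. It shows only how sensitive the rules are once a case occurs, not how often one will.

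**Conclusion.** The concern holds. On the text as supplied, the definition contradicts itself by 0.3°C (0.54°F), and no supplied section resolves it. How the one-hour condition applies is also open; this is the lesser point. Its size was not estimated, and it could affect fevers above both figures.

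The effect on dosing is conditional. It requires that the protocol's DLT section or the adjudication uses this wording, and that a qualifying case occurs. The documents give no frequency, and such cases are probably rare. When both conditions are met, one participant can change the Table 2 action, for example from escalate (0/3) to stay (1/3), or from escalate (1/6) to de-escalate (2/6).

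This should be fixed because it sits inside the definition of a primary endpoint. Nothing here says which temperature or duration rule is right; the documents do not show which was intended.

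**What to change.** 1. Check the SAP 10.1 line against the source PDF.
2. Reconcile it with the protocol's DLT section so that the Celsius and Fahrenheit figures are the same temperature, with the comparator stated.
3. State whether the one-hour duration applies and, if so, how it is to be established from recorded temperatures.
4. Use that one definition for all DLT adjudication, cohort decisions, summaries and listings.

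The cost is a one-line correction to the SAP, and to the protocol if it carries the same wording. No new data are needed.

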10.2 Adverse Events

All reported AEs will be coded using the Medical Dictionary for Regulatory Activities (MedDRA) with the most current version for the purposes of summarization. NCI CTCAE Version 5.0 will be used for grading AEs. AEs will be collected and recorded for each patient from the day of signing the ICF until 30 days after last trial intervention administration or until participant started alternative anticancer therapy, whichever is sooner. Prior to receiving trial intervention, only AEs considered related to trial procedures and all SAEs will be summarized by arm, dose level, and dose schedule.

A treatment-emergent adverse event (TEAE) will be defined as any event that was not present prior to the initiation of trial intervention(s) or any event that worsens in either intensity or frequency following exposure to trial intervention(s) through 30 days after cessation of trial treatment, or until the participant starts alternate anti-cancer therapy, or the participant is taking the monotherapy treatment and starts the co-therapy olaparib, whichever occurs first. The exception are RP-3467 related SAEs which were reported until the end of trial and will be included as TEAE regardless of time of onset.

All AEs reports will be summarized by treatment regimen (Arm 1 and Arm 2), dose level and schedule (if applicable) unless otherwise specified.

Overall AE summaries will be presented for the Safety Population (unless otherwise specified). The summaries will include the following categories:

- All TEAEs
- TEAEs with CTCAE Grade 3
- TEAEs with CTCAE Grade 4
- TEAEs with CTCAE Grade 5
- DLT (based on DLT evaluable population)
- RP-3467 related TEAE
 - RP-3467 related TEAE with CTCAE Grade 3
 - RP-3467 related TEAE with CTCAE Grade 4
 - RP-3467 related TEAE with CTCAE Grade 5
- Olaparib related TEAE
 - Olaparib related TEAE with CTCAE Grade 3
 - Olaparib related TEAE with CTCAE Grade 4
 - Olaparib related TEAE with CTCAE Grade 5
- Any Serious AEs
- Any treatment-emergent serious AEs (TESAE)
- RP-3467 related TESAEs
- TEAE leading to dose reduction
- TEAE leading to dose interruption
- TEAE leading to study drug withdrawal
- RP-3467 related TEAE leading to dose reduction
- RP-3467 related TEAE leading to dose interruption

- RP-3467 related TEAEs leading to study drug withdrawal
- Olaparib related TEAE leading to dose reduction
- Olaparib related TEAE leading to dose interruption
- Olaparib related TEAE leading to study drug withdrawal
- Adverse Event of Special interest (AESI) if any occurred as defined in the protocol
- TEAE leading to Death

Any missing onset date, causality, or severity must be queried for resolution. Unresolved missing causality will be considered “Related”.

Any missing or partial dates will be handled according to the rules outlined in section 5.4.

TEAEs will be summarized by SOC, PT unless stated otherwise. TESAEs, Related TEAEs, TEAEs leading to dose modification, TEAEs leading to drug withdrawn, TEAEs leading to death will be summarized in a similar manner.

Summaries tables will be sorted by decreasing frequency of subjects within each SOC and then similarly by decreasing frequency of subjects within each PT. In the case of equal frequency of number of subjects in SOCs or PTs, summaries will be sorted in descending order. Sorting will be based on the total frequency in the combination therapy arm for safety [REDACTED] summaries, and across both arms for all other tables, unless stated otherwise.

Myelodysplastic syndrome (MDS) or Acute myelogenous leukemia (AML) are considered AESIs. These are applicable only to participants treated with olaparib will be listed with details if they occur.

If a SOC or PT was reported more than once for a subject, the subject would only be counted once in the incidence for that SOC or PT.

All AEs, SAEs, DLTs, and will be listed by patient, along with information regarding onset, duration, relationship and severity to study drug, action taken with study drug, treatment of event, and outcome.

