5.2 Definition of Treatment Emergent Period

Unless otherwise stated, derivations of the worst post-treatment value will be assessed within the confines of the treatment emergent period, defined as the time from the start of study treatment, until 30 days after the last dose of RP-3467 or olaparib, the participant starts a subsequent anti-cancer therapy, or the participant is taking the monotherapy treatment and starts olaparib treatment, whichever occurs first.

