Review of dosing diary ^z				X		X		X	X	X		X			
AE assessment			During Screening, only AEs considered related to trial procedures or SAEs need to be reported. Following initiation of dosing AE to be collected through 30 days after the last dose of trial intervention or start of new anticancer therapy, whichever is earlier. SAEs believed to be due to trial treatment should be reported through the end of trial date or whenever the Investigator becomes aware thereafter.												
Concomitant medications/procedures			To be collected from the time of Screening visit through the Safety Follow-up visit												
Transfusion and growth factors			If administered, to be collected from the time of Screening visit through the Safety Follow-up visit												
Post-trial therapy data collection															X
Survival status															X
Secondary hematologic malignancy status															X

AE = adverse event; BID = twice daily; CA-125 = cancer antigen 15, CT = computed tomography; ctDNA = circulating tumor DNA; CXDX = Cycle X Day X, Disc of Trt = Discontinuation of treatment; ECG = electrocardiogram; ECOG = Eastern Cooperative Oncology Group; EOT = end of treatment; ICF = informed consent form; MRI = magnetic resonance imaging; NGS = next-generation sequencing; PCWG3 = Prostate Cancer Working Group 3; PE = physical examination; PK = pharmacokinetic; PSA = prostate-specific antigen; RECIST = Response Evaluation Criteria in Solid Tumors; SAE = serious adverse event;

WOCBP = women of childbearing potential

a. **Screening:** Screening Period extends from Day -30 to Day -3. Screening laboratory assessments (hematology, chemistry, urinalysis, and serum tumor marker) may be used as Day -2 assessments if performed within 48 hours of the first dose of trial intervention. ECOG performance status and PE that are completed within 24 hours of first dose of trial treatment may be used as Day -2 assessments. Procedures that are to be performed as part of the practice of medicine and which would be done whether or not trial

entry was contemplated, such as for diagnosis or treatment of a disease or medical condition, may be performed and the results subsequently used for determining trial eligibility without first obtaining consent. Participants must continue to meet eligibility criteria prior to the first dose of RP-3467 on Day -2.

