- b. **EOT Visit:** An End-of-Treatment visit will be conducted following the last dose of trial intervention and within +7 days of the discontinuation of treatment date. If a participant comes to the clinic to start a new cycle but the decision is made to discontinue treatment, that visit may be used as the EOT visit. The EOT visit should occur prior to the start of subsequent anticancer treatment.
- c. **Safety Follow-up:** Required for all participants who discontinued from treatment for whatever reason. The window for the Safety Follow-up visit will be 30 (+14) days from the last dose of trial intervention.
- d. **Long-Term Follow-Up:** Follow-up will be conducted at approximately 3, 6, 12, 18, and 24 months (\pm 14 days) after the discontinuation of treatment date. This follow-up will be conducted by telephone contact or standard method used by participating centers and agreed by the Sponsor. This does not require an in-person visit. Information regarding post-trial therapy, survival status, and hematologic malignancy diagnosis will be collected. The Long-term follow-up period may end sooner if a participant is diagnosed with a hematologic malignancy or if death is known to have occurred prior to 24 months.
- e. **C1D8 and C1D9:** A +2 day window is allowed for the C1D8 visit. If a window is used for C1D8, the same window should be used for C1D9.
- f. **CXD1:** The start of a new additional cycle should always coincide with the start of trial intervention administration for that cycle. A +3-day window is allowed for the start of new cycles, though cycles should never start early and should be at least 21 days in length. A -2 day window is allowed for the safety assessments scheduled for the CXD1 visit to enable flexibility with visit scheduling.
- g. **CXD8:** Hematology and vital signs to be assessed only on Cycles 2 and 3.
- h. **Molecular Eligibility:** NGS reports will be emailed to the Sponsor-approved central annotation group for central review to confirm molecular eligibility.
- i. **Abbreviated PE:** Starting at Cycle 2, abbreviated PE to be performed every 2 cycles (unless full PE necessary by Investigator judgment).
- j. **Vital Signs:** Blood pressure, heart rate, and temperature to be measured after the participant has been sitting for 5 minutes.

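### SAP 10.2 readmits late SAEs to the TEAE tables only if RP-3467 related, so in Arm 2 a late SAE attributed to olaparib alone is collected but not counted

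*SAP*

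**What the plan says.** SAP 10.2 counts events that arise or worsen "following exposure to trial intervention(s) through 30 days after cessation of trial treatment, or until the participant starts alternate anti-cancer therapy". For monotherapy participants the window also closes when olaparib is started. One exception follows: "The exception are RP-3467 related SAEs which were reported until the end of trial and will be included as TEAE", whatever their time of onset. Olaparib is not named in it.

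The AE assessment row of the Schedule of Activities (SAP 12, Tables 5 and 6) has a wider collection rule: "SAEs believed to be due to trial treatment should be reported through the end of trial date or whenever the Investigator becomes aware thereafter". Long-term follow-up contacts are also planned: "Follow-up will be conducted at approximately 3, 6, 12, 18, and 24 months" after discontinuation. At these, "Information regarding post-trial therapy, survival status, and hematologic malignancy diagnosis will be collected".

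The overall AE summary in SAP 10.2 gives related TEAEs, their Grade 3, 4 and 5 subsets, and related TEAEs leading to reduction, interruption and withdrawal for each drug separately. Related treatment-emergent SAEs (TESAEs) have a row for RP-3467 only. The list also has a row for any serious AE, not limited to treatment-emergent events, and an AESI row with no stated window. MDS and AML are the named AESIs, and the SAP adds: "These are applicable only to participants treated with olaparib will be listed with details if they occur".

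**The concern.** Incidence and severity of TEAEs form part of the primary endpoint (SAP 3.2.1), and the primary objective covers RP-3467 in combination with olaparib as well as alone (SAP 3.1.1). In Arm 2, whether a late serious event counts towards that endpoint depends on which drug the investigator names. Two participants with the same late event would be classified differently, although both events are collected under the same rule.

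The difference does not look deliberate. The rest of the TEAE definition speaks of trial intervention(s), which the protocol's exclusion criterion on hypersensitivity uses for both drugs. The schedule's collection rule makes no distinction by drug. At stake is a modest undercount of serious late toxicity in the combination arm's treatment-emergent tables. The summary list has a matching gap whatever the window: an olaparib-related TESAE has no row of its own.

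**Working it through.** The point is one of definition, and the plan states no figure to reproduce. The check applies the rules to each case, then sizes one event.

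**1. Arm 2 SAEs under the two rules** (collection: SAP 12, Tables 5 and 6; counting: SAP 10.2)

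| SAE onset and attribution | Collected | Counted as TEAE |
|---|---|---|
| Within the window, any attribution | Yes | Yes |
| After the window, RP-3467 alone | Yes | Yes, by the exception |
| After the window, both drugs | Yes | Yes, by the exception |
| After the window, olaparib alone | Yes | No |

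Only the last row is a gap. It needs three things together: a serious event, onset after the window, and attribution to olaparib alone.

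**2. Where the event goes**

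- Missing from: all TEAEs, TEAEs by grade, olaparib-related TEAEs (overall and by grade), TESAEs and, if fatal, TEAEs leading to death.
- Still present in: the any-serious-AE row and the SAE listing. MDS/AML reported as an event also appears in the AESI row and its detailed listing.

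**3. Timing of follow-up.** Using the SAP's 30.4375 days per month (SAP 6.4) and the 14-day tolerance, the earliest contact is at 3 × 30.4375 − 14 = 77.3 days. The later ones are at about days 169, 351, 534 and 717. All fall after day 30, so the plan does look for hematologic malignancy outside the window. A contact date shows when an event is found, however, and SAP 10.2 turns on when it arose or worsened.

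**4. Size of one event.** SAP 2.3 gives about 24 participants for Arm 2 escalation and 16 for backfill. SAP 2.1 describes backfill after an Arm 2 MTD, so I assume all 16 are in Arm 2.

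- Arm 2 overall: 1/(24 + 16) = 1/40 = 2.5%.
- Escalation only: 1/24 = 4.2%.
- One backfilled dose level, assuming 3 to 6 escalation participants plus 8 backfill: 1/11 = 9.1% to 1/14 = 7.1%.

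Each is the shift in the any-TESAE row for a participant with no other TESAE. A participant who has another stays in that row, and only the SOC or PT line for the late event can lose the count.

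**5. Chance that it arises.** The documents give no rate of late olaparib-only SAEs. For an assumed rate p per participant, the chance of at least one is 1 − (1 − p)^n:

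| Assumed p | n = 24 | n = 40 |
|---|---|---|
| 0.5% | 11% | 18% |
| 1% | 21% | 33% |
| 2% | 38% | 55% |
| 3% | 52% | 70% |

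The rates are illustrative only; the table shows how far the answer depends on them.

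**The case against.** The strongest reply is that little is lost. The analysis is descriptive (SAP 5). DLTs are confined to Cycle 1 (SAP 4.1 and 10.1), so escalation and the MTD do not depend on late events. Every SAE is listed with its relationship and outcome. All of this stands and limits the consequence. It does not remove the inconsistency, because a listing or an any-serious-AE row is not the TEAE incidence named as the endpoint.

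Three stronger readings are tempting, and the documents do not support them.

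- **That every MDS/AML first found in long-term follow-up is excluded.** Onset governs. A case that began within 30 days and before new anticancer therapy is a TEAE even if found at month 3. A completely missing start date is set to first dose (SAP 5.6), which makes the event treatment-emergent. Nor does tying the AESI to olaparib-treated participants say how investigators will attribute it; attribution to both drugs keeps the event in. Unresolved missing causality becomes related (SAP 10.2), though the SAP does not say to which drug.
- **That MDS/AML disappears from the report.** It has a summary row and a listing, neither limited to the TEAE window.
- **That one omitted case in a backfill cohort of 8 takes related-TESAE incidence from 12.5% to 0%.** The only related-TESAE row is for RP-3467, and an olaparib-only event never enters it. Nor is 8 a reporting denominator: tables are by arm, dose level and schedule (SAP 5), and a backfilled level also contains its escalation participants.

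The full protocol's AE-reporting section is not in the public text, so whether the SAP departs from it cannot be judged. The mismatch shown is between SAP 10.2 and the SAP's own appended schedule.

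**Conclusion.** The inconsistency is real, and nothing in the available text cures it. Followed as written, SAP 10.2 leaves late Arm 2 SAEs attributed to olaparib alone out of the treatment-emergent summaries, while counting the same events when RP-3467 is named. The direction is an undercount, limited to that class of event and those tables. One affected participant is worth 2.5% of Arm 2 on the assumptions above, and roughly 7% to 9% of a backfilled dose level. How often this will happen cannot be said from the documents. It should be corrected before the tables are produced; it does not threaten dose finding or hide the events from a reader of the listings.

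**What to change.** Three changes to SAP 10.2:

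1. For Arm 2, extend the late-SAE exception to SAEs related to RP-3467 or to olaparib, in line with the schedule's collection rule.
2. Add a row for olaparib-related TESAEs beside the RP-3467 one.
3. State that SAEs arising in the rescue period of Arm 1 participants who cross over to the combination are reported separately. Without this, an exception widened for both arms would bring olaparib-related events into the monotherapy columns, although the TEAE window for those participants is meant to close when olaparib starts. The existing exception, which ignores time of onset, already lets RP-3467-related rescue-period SAEs in.

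The period in SAP 5.2 has no late-SAE exception, but it governs worst post-treatment values and need not change for this purpose.

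The cost is SAP wording and table shells only, since the schedule already collects the events. Arm 2 serious-event counts may come out slightly higher.
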